| Body region | Erythema (E) | Thickening (plaque elevation, induration, I) | Scaling (desquamation, D) | Area score (based on true area %, A)* |
|------------------------------|---|---|---|--|
| Head (H) [†] | 0=none 1=slight 2=moderate 3=severe 4=very severe | 0=none 1=slight 2=moderate 3=severe 4=very severe | 0=none 1=slight 2=moderate 3=severe 4=very severe | 0=no involvement 1=>0-<10% 2=10-<30% 3=30-<50% 4=50-<70% 5=70-<90% 6=90-100% |
| Trunk (T) [‡] | 0=none 1=slight 2=moderate 3=severe 4=very severe | 0=none 1=slight 2=moderate 3=severe 4=very severe | 0=none 1=slight 2=moderate 3=severe 4=very severe | 0=no involvement 1=>0-<10% 2=10-<30% 3=30-<50% 4=50-<70% 5=70-<90% 6=90-100% |
| Upper limbs (U) | 0=none 1=slight 2=moderate 3=severe 4=very severe | 0=none 1=slight 2=moderate 3=severe 4=very severe | 0=none 1=slight 2=moderate 3=severe 4=very severe | 0=no involvement 1=>0-<10% 2=10-<30% 3=30-<50% 4=50-<70% 5=70-<90% 6=90-100% |
| Lower limbs (L) [§] | 0=none 1=slight 2=moderate 3=severe 4=very severe | 0=none 1=slight 2=moderate 3=severe 4=very severe | 0=none 1=slight 2=moderate 3=severe 4=very severe | 0=no involvement 1=>0-<10% 2=10-<30% 3=30-<50% 4=50-<70% 5=70-<90% 6=90-100% |

*Percentage (not score) of body region (not whole body) affected will be entered in the eCRF

[†]Neck is assessed as part of the Head (H) body region

[‡]Axillae and groin are assessed as part of the Trunk (T) body region

[§]Buttocks are assessed as part of the Lower limbs (L) body region

Definitions of efficacy variables based on PASI

The following definitions will be used in this study based on the CHMP guidelines for psoriasis (CHMP/EWP/2454/02 2004):

- **PASI 50 response:** subjects achieving $\geq 50\%$ improvement (reduction) in PASI score compared to baseline are defined as PASI 50 responders
- **PASI 75 response:** subjects achieving $\geq 75\%$ improvement (reduction) in PASI score compared to baseline are defined as PASI 75 responders
- **PASI 90 response:** subjects achieving $\geq 90\%$ improvement (reduction) in PASI score compared to baseline are defined as PASI 90 responders
- **PASI 100 response / remission:** complete clearing of psoriasis (PASI=0)

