Based on these considerations and the fact that we are looking at PASI90 response in the present study, we assume an absolute increase of 9% in PASI90 response in the Secukinumab combined with lifestyle intervention arm to 90% PASI90 responders compared to 81% PASI90 responders in the Secukinumab alone arm. An absolute increase of 9% in PASI90 responders would also be clinically meaningful.

Based on these assumptions 342 patients per arm would provide a power of 90 % at a two-sided alpha of 0.05 to demonstrate that the percentage of PASI90 responders at week 28 is higher in

the Secukinumab combined with lifestyle intervention arm compared to the Secukinumab alone arm. In case the true effect size would only be 7.5 %, this sample size would still provide a power of 75 %. To compensate for some expected drop out and/or premature discontinuations, 380 patients per arm are planned to be recruited for this trial.

10 Ethical considerations

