2.5 Analysis of the primary objective

2.5.1 Primary endpoint

The primary variable is the percentage of patients achieving PASI90 at week 28 in both randomized treatment arms, Secukinumab alone and Secukinumab combined with lifestyle intervention.

The primary analysis will be to demonstrate that the combination of Secukinumab (300 mg, 4-weekly s.c.) with lifestyle intervention results in higher psoriasis treatment efficacy than Secukinumab alone with respect to the primary endpoint in the FAS.

PASI score will be derived as indicated in Table 2-1. The head, trunk, upper limbs and lower limbs are assessed separately for erythema, thickening (plaque elevation, induration), and scaling (desquamation). The average degree of severity of each sign in each of the four body regions is assigned a score of 0-4. The area covered by lesions on each body region is estimated as a percentage of the total area of that particular body region. Further practical details to help with the assessment are provided below:

1. The neck is assessed as part of the head
2. The axillae and groin are assessed as part of the trunk
3. The buttocks are assessed as part of the lower limbs
4. When scoring the severity of erythema, scales should not be removed

Because the head and neck, upper limbs, trunk and lower limbs correspond to approximately 10%, 20%, 30% and 40% of the body surface area, respectively, the PASI score is calculated using the formula:

$$\text{PASI} = 0.1(\text{E}_\text{H} + \text{I}_\text{H} + \text{D}_\text{H})\text{A}_\text{H} + 0.2(\text{E}_\text{U} + \text{I}_\text{U} + \text{D}_\text{U})\text{A}_\text{U} + 0.3(\text{E}_\text{T} + \text{I}_\text{T} + \text{D}_\text{T})\text{A}_\text{T} + 0.4(\text{E}_\text{L} + \text{I}_\text{L} + \text{D}_\text{L})\text{A}_\text{L}$$

The keys for the letters are provided in Table 2-1.

PASI scores can range from a lower value of 0, corresponding to no signs of psoriasis, up to a theoretic maximum of 72.0.

The baseline value for analysis of the PASI is collected at the Randomization Visit.

Table 2-1 The PASI scoring system

Body Region	Erythema (E)	Thickening (plaque elevation, induration, I)	Scaling (desquamation, D)	Area score (based on true area %, A)*
Head(H) †	0=none	0=none	0=none	0=no involvement
	1=slight	1=slight	1=slight	1=>0-<10%
	2=moderate	2=moderate	2=moderate	2=>10-<30%
	3=severe	3=severe	3=severe	3=>30-<50%
	4=very severe	4=very severe	4=very severe	4=>50-<70%
				5=>70-<90%
				6=>90-100%

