Trunk(T) ‡	0=none	0=none	0=none	0=no involvement
	1=slight	1=slight	1=slight	1=>0-<10%
	2=moderate	2=moderate	2=moderate	2=>10-<30%
	3=severe	3=severe	3=severe	3=>30-<50%
	4=very severe	4=very severe	4=very severe	4=>50-<70%
				5=>70-<90%
				6=>90-100%
Upper limbs (U)	0=none	0=none	0=none	0=no involvement
	1=slight	1=slight	1=slight	1=>0-<10%
	2=moderate	2=moderate	2=moderate	2=>10-<30%
	3=severe	3=severe	3=severe	3=>30-<50%
	4=very severe	4=very severe	4=very severe	4=>50-<70%
				5=>70-<90%
				6=>90-100%
Lower limbs (L) §	0=none	0=none	0=none	0=no involvement
	1=slight	1=slight	1=slight	1=>0-<10%
	2=moderate	2=moderate	2=moderate	2=>10-<30%
	3=severe	3=severe	3=severe	3=>30-<50%
	4=very severe	4=very severe	4=very severe	4=>50-<70%
				5=>70-<90%

Body Region	Erythema (E)	Thickening (plaque elevation, induration, I)	Scaling (desquamation, D)	Area score (based on true area %, A)*
				6=>90-100%

*Percentage (not score) of body region (not whole body) affected will be entered in the eCRF †Neck is assessed as part of the Head (H) body region

‡Axillae and groin are assessed as part of the Trunk (T) body region

§Buttocks are assessed as part of the Lower limbs (L) body region

Definitions of efficacy variables based on PASI

The following definitions will be used in this study:

- **PASI 50 response:** subjects achieving $\geq 50\%$ improvement (reduction) in PASI score compared to baseline are defined as PASI 50 responders
- **PASI 75 response:** subjects achieving $\geq 75\%$ improvement (reduction) in PASI score compared to baseline are defined as PASI 75 responders
- **PASI 90 response:** subjects achieving $\geq 90\%$ improvement (reduction) in PASI score compared to baseline are defined as PASI 90 responders
- **PASI 100 response / remission:** complete clearing of psoriasis (PASI=0)

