2.5.3 Handling of missing values/censoring/discontinuations

Patients who do not have a valid PASI assessment at week 28 will be regarded as non-responders for the primary analysis.

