Based on these assumptions 342 patients per arm would provide a power of 90 % at a two-sided alpha of 0.05 to demonstrate that the percentage of PASI90 responders at week 28 is higher in the Secukinumab combined with lifestyle intervention arm compared to the Secukinumab alone arm. In case the true effect size would only be 7.5 %, this sample size would still provide a power of 75 %. To compensate for some expected drop out and/or premature discontinuations, 380 patients per arm are planned to be recruited for this study.

4 Change to protocol specified analyses

Below mentioned changes to the analysis described in Section 9 of the protocol version 02 are planned.

- i. Separate analyses will be performed for subjects with fasting and non-fasting status for fasting plasma glucose, fructosamine, and HbA1c in secondary analyses
- ii. Separate analyses will be performed for subjects with fasting and non-fasting status for all the biomarkers in biomarker sub-study
- iii. Additional analysis proposed for stratification of the analysis for PASI 75, PASI 90, PASI 100 and all study biomarkers by the groups “patients achieving weight loss < 5%”, “patients achieving weight loss $\geq 5\%$ - < 10%” and “patients achieving weight loss $\geq 10\%$ ” in each treatment arm.

5 Appendix

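### SAP Table 2-1, read literally, gives no PASI area score to a body region exactly 10, 30, 50, 70 or 90% affected, whereas the protocol scores all five values

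*Protocol*

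**What the plan says.** Protocol 6.4.1, Table 6-2, uses the same area classes for head, trunk, upper limbs and lower limbs: "0=no involvement 1=>0-<10% 2=10-<30% 3=30-<50% 4=50-<70% 5=70-<90% 6=90-100" per cent. Each class from 2 upward includes its lower limit. The footnote to that table says "Percentage (not score) of body region (not whole body) affected will be entered in the eCRF", and the SAP repeats it.

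Section 2.5.1 of the core-study SAP says "PASI score will be derived as indicated in Table 2-1". In that table the lower limits of classes 2 to 6 carry a greater-than sign (above 10, above 30, above 50, above 70, above 90). The upper limits of classes 1 to 5 remain strict (below 10, below 30, below 50, below 70, below 90). The pattern is the same in all four regions.

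PASI90 response is a reduction of at least 90% from baseline PASI. On missing data, SAP 2.5.3 says "Patients who do not have a valid PASI assessment at week 28 will be regarded as non-responders for the primary analysis". SAP 2.1.1.2 substitutes the Visit 1 measurement when Visit 2 is missing. SAP section 4 opens with "Below mentioned changes to the analysis described in Section 9 of the protocol version 02 are planned" and lists three items: two on fasting status and one on weight-loss subgroups. None concerns PASI scoring.

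**The concern.** The two documents give different scoring rules for the sole primary endpoint, and the SAP's rule has gaps. Since the site enters a percentage, the area score has to be assigned from a table, and the SAP points to its own.

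PASI at baseline and at Week 28 together determine PASI90. Baseline PASI is also the covariate in the primary logistic model (SAP 2.5.2 and 5.2.1). The PASI75/90/100 and absolute PASI analyses in SAP 2.6.1 and 2.8 use the same score. If the table were programmed as printed, one region on a boundary would be enough to leave a patient's total PASI underived at that visit.

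**Working it through.** **1. The two tables side by side**

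Inputs are the class limits in Protocol Table 6-2 and SAP Table 2-1. Scoring every whole percentage from 0 to 100 under both tables gives the same result everywhere except at five values:

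| Region affected | Protocol | SAP, literal | Code testing the SAP's lower limits from the top down | Code testing the SAP's upper limits from the bottom up |
|---|---|---|---|---|
| 10% | 2 | none | 1 | 2 |
| 30% | 3 | none | 2 | 3 |
| 50% | 4 | none | 3 | 4 |
| 70% | 5 | none | 4 | 5 |
| 90% | 6 | none | 5 | 6 |

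The last two columns are ways a programmer might close the gap. The first contradicts the SAP's own strict upper limits. The second reproduces the protocol.

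**2. What a boundary value does to one patient**

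Formula (both documents): PASI = sum over regions of weight × (E+I+D) × area score, with weights 0.1 head, 0.2 upper limbs, 0.3 trunk and 0.4 lower limbs. The two patients below are invented.

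*Boundary at baseline.* Head 10% with E+I+D = 6; the other three regions 30% with E+I+D = 7. Week 28 PASI is 1.8.
- Protocol: 0.1×6×2 + 0.9×7×3 = 1.2 + 18.9 = 20.1. Reduction 1 − 1.8/20.1 = 91.0%, responder.
- SAP literal: baseline PASI not derivable.
- Class below: 0.1×6×1 + 0.9×7×2 = 0.6 + 12.6 = 13.2. Reduction 1 − 1.8/13.2 = 86.4%, non-responder.

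*Boundary at Week 28.* Baseline head 35% with E+I+D = 6; the other three regions 60% with E+I+D = 9. Baseline PASI = 0.1×6×3 + 0.9×9×4 = 34.2 under both tables. At Week 28, upper limbs 5% with E+I+D = 3 and lower limbs 10% with E+I+D = 4.
- Protocol: 0.2×3×1 + 0.4×4×2 = 0.6 + 3.2 = 3.8. Reduction 1 − 3.8/34.2 = 88.9%, non-responder.
- SAP literal: Week 28 PASI not derivable, so non-responder if treated as having no valid assessment.
- Class below: 0.6 + 0.4×4×1 = 2.2. Reduction 1 − 2.2/34.2 = 93.6%, responder.

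The misclassification can therefore go either way.

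**3. Scale, under an explicit assumption**

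Protocol 9.8 states "Based on these assumptions 342 patients per arm would provide a power of 90 % at a two-sided alpha of 0.05", for "90% PASI90 responders compared to 81% PASI90 responders in the Secukinumab alone arm". The pooled two-proportion formula gives 320 per arm without and 342 with a continuity correction, so the stated figure is reproduced. With

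power = Φ{[d − 1/n − 1.96·√(2p̄(1−p̄)/n)] / √[(p₁(1−p₁)+p₂(1−p₂))/n]}

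and n = 342, power is 90.1% for 81% against 90% and 74.7% for 81% against 88.5% (stated: 90% and 75%).

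Suppose a share s of would-be responders in both arms were counted as non-responders because PASI could not be derived, so that the rates become 0.81(1−s) and 0.90(1−s):

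| s (assumed) | Rates | Power |
|---|---|---|
| 0% | 81.0% vs 90.0% | 90% |
| 2% | 79.4% vs 88.2% | 86% |
| 5% | 77.0% vs 85.5% | 79% |
| 10% | 72.9% vs 81.0% | 68% |

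No value of s can be taken from the documents.

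**The case against.** The strongest reply is that nothing need go wrong in practice.

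- **The protocol settles the matter.** It scores every percentage, the SAP presents itself as implementing the protocol, and no departure is declared. A reader might infer that the endpoint is undefined; that goes too far, because the protocol still defines it. What stands is that the SAP names its own table as the source of PASI and that table has gaps.
- **The program may be right.** Code chained on the SAP's upper limits gives exactly the protocol's scores. The documents do not show the program, so this can be neither confirmed nor excluded.
- **The sign may have been meant as at least.** The equals sign followed by a greater-than sign could be a typed or badly converted symbol. Against this, the equals sign separates label from meaning throughout the table, and class 1 must be strict because 0 is its own class. That second argument is weak: a region without lesions contributes zero whichever class it is given. The intended reading cannot be fully excluded, but a scoring rule open to two readings still needs correction.
- **A missing baseline has a fallback.** SAP 2.1.1.2 uses Visit 1, so a boundary value at Visit 2 does not by itself leave the patient without a baseline. Visit 1 is scored from the same table, however, and may hold boundary values too.

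A reader might also infer that the table systematically under-scores baseline and turns responders into non-responders, or that many patients are affected because raters favour round numbers. The documents support neither. The class below is excluded by the SAP's own upper limits, the second invented patient shows the opposite change, and no distribution of entered percentages or rounding habit is given.

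**Conclusion.** SAP Table 2-1 is wrong as written. Taken literally, it leaves exactly 10, 30, 50, 70 and 90% without an area score in all four regions, contrary to Protocol Table 6-2 and without a declared change; a transcription error is the likely explanation. The rule feeds the primary endpoint, its baseline covariate and the secondary PASI analyses, so the discrepancy is more than clerical.

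The consequence depends on code that the documents do not show: correct scores, an underived PASI, or a score shifted in either direction. The frequency of boundary values is also unknown, so any size, including the power range above, is an assumption. The same rule applies to both arms, and nothing in the documents shows a bias in the comparison. On the assumed scenarios, the cost would be loss of power.

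**What to change.** In SAP Table 2-1, restore the protocol's limits for all four regions: 1 = >0 to <10%, 2 = 10 to <30%, 3 = 30 to <50%, 4 = 50 to <70%, 5 = 70 to <90%, 6 = 90 to 100%. Test the PASI derivation program at 0, 10, 30, 50, 70, 90 and 100%, expecting 0, 2, 3, 4, 5, 6 and 6, and file the result. If analyses have already been run, confirm and record which limits were used.

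The cost is five corrected lines per region in one table and a short program check. No new data are needed, and the sample size of 342 per arm for analysis does not change.

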6.4.2 Biomarkers of glucose and lipid metabolism

Biomarkers of glucose metabolism: HbA1c, fructosamine and fasting plasma glucose.

Biomarkers of lipid metabolism: Total cholesterol, triglycerides, LDL, HDL.

These markers will be assessed as part of the routine or fasting laboratory, time points are shown in table 6-1.

6.4.3 Biomarkers of systemic inflammation

Biomarker of systemic inflammation: hsCRP

This marker will be assessed as part of the routine laboratory, time points are shown in table 6-1.

6.4.4 Weight and height

Height and body weight will be measured as listed in table 6-1, height in centimeters (cm) and body weight in kilogram (kg) (to the nearest 0,1 kg).

Height and body weight will be measured in indoor clothing, but without shoes. Whenever possible, body weight assessment should be performed by the same study site staff member; the same scale should be used throughout the study.

6.4.5 Waist and hip circumference

Waist and hip circumference will be measured as listed in table 6-1, both in centimeters (cm).

Waist circumference measurement is taken with a tape measure at the approximate midpoint between the inferior margin of the last palpable rib and the top of the iliac crest (as suggested by WHO and IDF). The accuracy of waist and hip circumference measurements depends on correct tightness and positioning of the measuring tape: Measurements should be made with a **stretch-resistant tape**, which should be snug around the body **parallel to the floor/ in a horizontal plane**. The tape should **not** be pulled so that tight that it is constricting. A standardized tape supplied by Novartis has to be used.

6.4.6 Blood pressure and pulse

Resting blood pressure will be assessed at every scheduled visit as indicated in Table 6-1 according to the 2013 European Society for Cardiology guidelines for the management of arterial hypertension (Mancia et al., 2013). Whenever possible, assessments should be performed by the same study site staff member throughout the study. **It is crucial that blood pressure is measured in the resting state and therefore appropriate resting conditions are ensured:**

Coffee, black tea, caffeine and smoking must be avoided before the measurement is performed. **After the subject has been sitting and resting in a quiet environment for five minutes,** with back supported and both feet placed on the floor, systolic and diastolic **blood pressure will be measured twice (measurements separated by 2 minutes)** using an **automated, validated device**, with an appropriately sized cuff. A standard bladder (12-13 cm wide and 35 cm long) should be used, but a larger and a smaller bladder have should be available for large (arm circumference >32 cm) and thin arms. The cuff should be at the heart level of the patient. Measurements will be recorded in the source documentation and **the average of the two**

measurements will be entered on the Vital Signs eCRF. The same applies for the pulse measurement.

6.4.7 Appropriateness of efficacy assessments

PASI/ BSA: PASI scores outcome measures, the assessment of the severity of the psoriasis symptoms and the extent to which the subject's body area is affected by the disease, is mandated by the EMA for the clinical investigation of medicinal products for the treatment of psoriasis (CHMP/EWP/2454/02 2004).

Biomarkers of glucose: HbA1c and fasting plasma glucose are standard parameters used in daily clinical practice to monitor glucose metabolism and recommended in German national guidelines for diagnosis of diabetes (Kerner et al., 2014). Fructosamine is not as widely used as HbA1c or fasting plasma glucose but offers the advantage of indicating the quality of glucose control during the last 2-3 weeks in contrast to HbA1c, which is an indicator of glucose control during the last 8-12 weeks (Ribeirio et al., 2016).

Biomarkers of lipid metabolism: total cholesterol, triglycerides, HDL and LDL are standard parameters used in daily clinical practice to monitor lipid status and assess cardiovascular risk profile. They are recommended in European guidelines for diagnosis and management of dyslipidemias (Reiner et al., 2011).

CRP is the most widely used blood marker of systemic inflammation. The detection method used for the hsCRP test allows more sensitive testing and was used in several psoriasis clinical trials as a marker of systemic inflammation (Puig et al., 2014; Gkalpakiotis et al., 2016).

Weight, BMI and hip circumference are clinical routine parameters for the assessment of obesity. Measurement of systolic and diastolic blood pressure is clinical routine for the assessment of hypertension.

6.5 Safety

Blood withdrawals and safety assessments should be done prior to study treatment administration. Appropriate safety assessments (e.g. evaluation of AEs and SAEs including injection site reactions) should be repeated after the dose is administered. Several of the safety parameters are used as efficacy parameters as well and are therefore already described in the section 6.4 above (e.g. hsCRP, blood pressure, body weight).

6.5.1 Physical examination

A physical examination, including general appearance, skin, neck, eyes, ears, nose, throat, lungs, heart, abdomen, back, lymph nodes, extremities, vascular and neurological systems will be performed as indicated in Table 6-1.

If necessary, based on medical history and/or symptoms, additional exams will be performed at the discretion of the investigator.

Whenever possible, assessments for an individual subject should be performed by the same member of the study site staff throughout the study.

6.5.2 Vital signs

Vital signs (blood pressure and pulse measurements) will be assessed at every scheduled visit as indicated in Table 6-1. Whenever possible, assessments should be performed by the same study site staff member throughout the study. Please see detailed description of blood pressure measurement in section 6.4.6.

6.5.3 Height and weight

Height and body weight will be measured as listed in Table 6-1, height in centimeters (cm) and body weight in kilogram (kg) (to the nearest 0,1 kg).

Measurement is described in detail in section 6.4.4.

6.5.4 Laboratory evaluations

A central laboratory will be used for analysis of all specimens listed below, unless noted otherwise. Details on the collections, shipment of samples and reporting of results by the central laboratory are provided to investigators in the laboratory manual. Refer to the Laboratory Manual for identification of laboratory reference range values and the schema for notification of site staff and Novartis for out of range values.

Except for liver and renal laboratory values, no specific action is pre-defined within this protocol to respond to specific abnormal laboratory values, as it will be decided by the investigator whether and which specific action needs to be taken to respond to any abnormal values, taking into account the overall status of the subject.

